10.7.4.2. Scientific Rationale for Substudy A Design

See Section 10.7.2.1.

10.7.4.2.1. Statistical Rationale for Substudy A Design

In addition to assessing the safety of administering a booster dose in a large number of participants, a key objective of this study is to characterize the potential for waning VE over time in participants who do not receive a booster. It is important to identify when a booster is needed to protect the participants in this trial, as well as to inform vaccine policy decision-makers. Consequently, the most appropriate statistical framework to facilitate decision-making in this setting is periodic statistical summaries (every 2 months over the scheduled 6-month follow-up period) using statistical guidelines, rather than the traditional hypothesis testing framework with strong control of overall type 1 error across analysis time points.

Using a traditional hypothesis testing framework, a policy of recommending a booster would be implemented only if the lower limit of the alpha-adjusted CI for VE of the boosted group relative to the unboosted group was greater than some specified value (eg, 20% or 30%). This approach controls the overall type 1 error, that is, deciding that a booster is necessary to maintain VE when it is actually not necessary. But strong control of type 1 error inflates type

2 error for a fixed sample size. And in this setting, type 2 error, that is, deciding that a booster is not necessary when it actually is, has a greater negative impact on public health.

For this reason, a descriptive statistical approach will be used with point estimates of VE (boosted relative to unboosted) and unadjusted (for multiplicity) 95% CIs at each time point (2, 4, and 6 months). In addition, to help put these results into perspective, an inferred VE for the unboosted group (relative to an unvaccinated population) will be calculated. Specifically, assuming that the newly boosted group has the same VE (relative to an unvaccinated population) over time that was observed in the parent C4591001 trial, an inferred unvaccinated (placebo) disease rate can be obtained at various time points and used to calculate the inferred VE (relative to unvaccinated) for the unboosted group. If this value is lower than a specified value (eg, 60%) at a given analysis time point, then a decision to offer a booster to the unboosted participants at that time may be implemented.

10.7.4.2.2. Diversity of Study Population

Reasonable attempts will be made to enroll participants with the distribution of characteristics shown to reflect that achieved in C4591001.⁴⁰

10.7.4.3. Justification for Dose

See Section 4.3 for a justification of the BNT162b2 dose used in Substudy A.

10.7.4.4. End of Study Definition

See Section 4.4.

10.7.5. Study Population

Details of the master eligibility criteria are shown in Section 5. Participants must meet all of the general inclusion and exclusion criteria as specified for both the master protocol and Substudy A–specific inclusion and exclusion criteria.

10.7.5.1. Inclusion Criteria

Participants are eligible to be included in Substudy A only if all of the following criteria apply:

Age and Sex:

1. Male or female participants ≥16 years of age at Visit 1 (Day 1) who participated in Study C4591001.

Refer to Appendix 4 for reproductive criteria for male (Section 10.4.1) and female (Section 10.4.2) participants.

Type of Participant and Disease Characteristics:

2. Participants who are willing and able to comply with all scheduled visits, vaccination plan, laboratory tests, lifestyle considerations, and other study procedures.

3. Healthy participants who are determined by medical history, physical examination (if required), and clinical judgment of the investigator to be eligible for inclusion in the study.

Note: Healthy participants with preexisting stable disease, defined as disease not requiring significant change in therapy or hospitalization for worsening disease during the 6 weeks before enrollment, can be included. Specific criteria for participants with known stable infection with HIV, HCV, or HBV can be found in Section 10.15.

Informed Consent:

4. Capable of giving personal signed informed consent/assent, have parent(s)/legal guardian capable of giving signed informed consent as described in Appendix 1, which includes compliance with the requirements and restrictions listed in the ICD and in this protocol.

The investigator, or a person designated by the investigator, will obtain written/electronically signed informed consent (and assent) from each study participant's legal guardian (as defined in Appendix 1), and the participant's assent, when applicable, before any study-specific activity is performed, unless a waiver of informed consent has been granted by an IRB/EC. All legal guardians should be fully informed, and participants should be informed to the fullest extent possible, about the study in language and terms they are able to understand. The investigator will retain the original copy of each participant's signed consent/assent document.

Other Inclusions:

5. Participants who have received 2 prior doses of 30 µg BNT162b2 19 to 42 days apart, with the second dose being at least 175 days before Visit 1 (Day 1).

Documented confirmation of prior BNT162b2 receipt must be obtained prior to randomization.

10.7.5.2. Exclusion Criteria

Participants are excluded from Substudy A if any of the following criteria apply:

Medical Conditions:

- 1. Other medical or psychiatric condition including recent (within the past year) or active suicidal ideation/behavior or laboratory abnormality that may increase the risk of study participation or, in the investigator's judgment, make the participant inappropriate for the study.
- 2. History of severe adverse reaction associated with a vaccine and/or severe allergic reaction (eg, anaphylaxis) to any component of the study intervention(s).

- 3. Previous clinical (based on COVID-19 symptoms/signs alone, if a SARS-CoV-2 NAAT result was not available) or microbiological (based on COVID-19 symptoms/signs and a positive SARS-CoV-2 NAAT result) diagnosis of COVID-19.
- 4. Immunocompromised individuals with known or suspected immunodeficiency, as determined by history and/or laboratory/physical examination.
- 5. Bleeding diathesis or condition associated with prolonged bleeding that would, in the opinion of the investigator, contraindicate intramuscular injection.
- 6. Women who are pregnant or breastfeeding.

Prior/Concomitant Therapy:

- 7. Individuals who receive treatment with radiotherapy or immunosuppressive therapy, including cytotoxic agents or systemic corticosteroids (if systemic corticosteroids are administered for ≥14 days at a dose of ≥20 mg/day of prednisone or equivalent), eg, for cancer or an autoimmune disease, or planned receipt throughout the study. Inhaled/nebulized, intra-articular, intrabursal, or topical (skin or eyes) corticosteroids are permitted.
- 8. Receipt of blood/plasma products, immunoglobulin, or monoclonal antibodies, from 60 days before study intervention administration, or receipt of any passive antibody therapy specific to COVID-19, from 90 days before study intervention administration, or planned receipt throughout the study.

Prior/Concurrent Clinical Study Experience:

9. Prior receipt of any COVID-19 vaccine other than BNT162b2.

Other Exclusions:

- 10. Investigator site staff or Pfizer-BioNTech employees directly involved in the conduct of the study, site staff otherwise supervised by the investigator, and their respective family members.
- 11. Receipt of medications intended to prevent COVID-19.
- 12. Prior receipt of more than 2 doses of BNT162b2 30 µg.
- 13. Participation in other studies involving study intervention within 28 days prior to study entry, other than C4591001, and/or within 28 days of confirmed receipt of BNT162b2 within the study.

10.7.5.3. Lifestyle Considerations

Contraception requirements will apply to Substudy A as detailed in Section 5.3 and Section 10.4.

10.7.5.4. Screen Failures

See Section 5.4.

10.7.5.5. Criteria for Temporarily Delaying Enrollment/Randomization/Administration of Study Intervention

See Section 5.5.

10.7.6. Study Intervention(s) and Concomitant Therapy

For the purposes of this substudy, study intervention refers to:

- BNT162b2 (BNT162 RNA-LNP vaccine utilizing modRNA and encoding the P2 S): 30 μg
- Normal saline (0.9% sodium chloride solution for injection)

10.7.6.1. Study Intervention(s) Administered

See Section 6.1 for details of BNT162b2.

| Additional Intervention Name | Saline Placebo |
|---------------------------------|--|
| Type | Placebo |
| Dose Formulation | Normal saline (0.9% sodium chloride solution for injection) |
| Unit Dose Strength(s) | N/A |
| Dosage Level(s) | N/A |
| Route of Administration | Intramuscular injection |
| Use | Placebo |
| IMP or NIMP | IMP |
| Sourcing | Provided centrally by the sponsor |
| Packaging and Labeling | Study intervention will be provided in a glass or plastic vial as open-label supply. Each vial will be labeled as required per country requirement |

10.7.6.1.1. Administration

Participants will receive 1 dose of study intervention at Visit 1 in accordance with the substudy's SoA (Section 10.7.1.3).

Study intervention at the booster vaccination visit should be administered intramuscularly into the deltoid muscle, preferably of the nondominant arm, by an **unblinded** administrator.

Study intervention administration at Visit 101 will be conducted in an open-label manner.

10.7.6.1.2. Preparation and Dispensing

For booster vaccination during Substudy A, study intervention will be prepared by qualified unblinded site personnel according to the IP manual. The study intervention will be administered in such a way as to ensure that the participants remain blinded.

10.7.6.2. Measures to Minimize Bias: Randomization and Blinding

10.7.6.2.1. Blinding of Site Personnel

In this observer-blinded substudy, the study staff receiving, storing, dispensing, preparing, and administering the study interventions will be unblinded. All other study and site personnel, including the investigator, investigator staff, and participants, will be blinded to study intervention assignments. In particular, the individuals who evaluate participant safety will be blinded. Because there are differences in physical appearance of the study interventions, the study intervention will be administered in a manner that prevents the study participants from identifying the study intervention group based on its appearance.

The PI will assign the responsibility of the unblinded dispensers/administrators to persons who will not participate in the evaluation of any study participant. To ensure adequate coverage, at least 2 unblinded dispensers/administrators will be assigned per site. Members of the study site staff or clinic pharmacy should fulfill these roles. Contact between the unblinded dispensers and study participants should be kept to a minimum. The investigator, study coordinator, and any site staff other than the unblinded dispensers/administrators must not be allowed to know the study intervention assigned to any study participant and must not be allowed to see the study intervention container contents. In the event of a Quality Assurance audit, the auditor(s) will be allowed access to unblinded study intervention records at the site(s) to verify that randomization/dispensing has been done accurately.

The study will be unblinded to site personnel at a time informed by the outcome of the interim analyses, as detailed in Section 10.7.9.4, or at a time decided by the sponsor.

10.7.6.2.2. Blinding of the Sponsor

The majority of sponsor/Pfizer staff will be blinded to study intervention allocation. All laboratory testing personnel performing serology assays will remain blinded to study intervention assigned/received throughout the study. The following sponsor/Pfizer staff, who will have no part in the blinded conduct of the study, will be unblinded (further details will be provided in a data blinding plan):

- Those study team members who are involved in ensuring that protocol requirements for study intervention preparation, handling, allocation, and administration are fulfilled at the site will be unblinded for the duration of the study (eg, unblinded study manager, unblinded clinical research associate).
- Unblinded clinician(s), who are not direct members of the study team and will not
 participate in any other study-related activities, will review unblinded protocol
 deviations.

- An unblinded team supporting interactions with, and analyses for, the DMC (see Section 10.7.9.4.2). This team comprises a statistician, programmer(s), a clinical scientist, and a medical monitor who will review cases of severe COVID-19 as they are received.
- An unblinded submissions team will be responsible for preparing unblinded analyses and documents to support regulatory activities that may be required while the study is ongoing. With the exception of the statisticians and programmers, who will become unblinded at the participant level at the time of the first planned reporting event to perform the analyses, other members of this team will only be unblinded at the group level and not have access to individual participant assignments. A separate group of statisticians and programmers will remain blinded and continue supporting the blinded conduct of the study after the first planned analysis.
- After the study data used for submission become public, the blinded study team will also have access to those data and become unblinded at a group level.
- The study will be unblinded to all sponsor/Pfizer staff at a time informed by the outcome of the interim analyses, as detailed in Section 10.7.9.4, or at a time decided by the sponsor.

10.7.6.2.3. Breaking the Blind

The IRT will be programmed with blind-breaking instructions. In case of an emergency, the investigator has the sole responsibility for determining if unblinding of a participant's study intervention assignment is warranted. Participant safety must always be the first consideration in making such a determination. If the investigator decides that unblinding is warranted, the investigator should make every effort to contact the sponsor prior to unblinding a participant's vaccine assignment unless this could delay further management of the participant. If a participant's vaccine assignment is unblinded, the sponsor must be notified within 24 hours after breaking the blind. The date and reason that the blind was broken must be recorded in the source documentation and CRF.

The study-specific IRT reference manual and IP manual will provide the contact information and further details on the use of the IRT system.

10.7.6.3. Study Intervention Compliance

See Section 6.4.

10.7.6.4. Dose Modification

See Section 6.5.

10.7.6.5. Continued Access to Study Intervention After the End of the Study

See Section 6.6.

10.7.6.6. Treatment of Overdose

See Section 6.7.

10.7.6.7. Concomitant Therapy

See Section 6.8.

10.7.7. Discontinuation of Study Intervention and Participant Discontinuation/Withdrawal

See Section 7.

10.7.8. Study Assessments and Procedures

The total blood sampling volume for individual participants in this study is up to approximately 60 mL.

For all participants, other additional blood samples may be taken for safety assessments at times specified by Pfizer, provided the total volume taken during the study does not exceed 550 mL during any period of 60 consecutive days.

10.7.8.1. Efficacy and/or Immunogenicity Assessments for Substudy A

10.7.8.1.1. Efficacy Against COVID-19

Efficacy will be assessed throughout a participant's involvement in the study through surveillance for potential cases of COVID-19. If, at any time, a participant develops acute respiratory illness (see Section 10.7.8.5.5.1), for the purposes of the study he or she will be considered to potentially have COVID-19 illness. In this circumstance, the participant should contact the site, an in-person or telehealth visit should occur, and assessments should be conducted as specified in the SoA. The assessments will include a nasal (midturbinate) swab, which will be tested at a central laboratory using an RT-PCR test (Cepheid; FDA-approved under EUA and Pfizer-validated), or other equivalent nucleic acid amplification—based test (ie, NAAT) to detect SARS-CoV-2. In addition, clinical information and results from local standard-of-care tests (as detailed in Section 10.7.8.5.5.1) will be assessed. The central laboratory NAAT result will be used for the case definition, unless no result is available from the central laboratory, in which case a local NAAT result may be used if it was obtained using 1 of the following assays:

- Cepheid Xpert Xpress SARS-CoV-2
- Roche cobas SARS-CoV-2 real-time RT-PCR test (EUA200009/A001)
- Abbott Molecular/RealTime SARS-CoV-2 assay (EUA200023/A001)

Definitions of SARS-CoV-2—related cases, and SARS-CoV-2—related severe cases, will be considered as follows (for both, the onset date of the case will be the date that symptoms were first experienced by the participant; if new symptoms are reported within 4 days after resolution of all previous symptoms, they will be considered as part of a single illness):

- Confirmed COVID-19: presence of at least 1 of the following symptoms and SARS-CoV-2 NAAT-positive during, or within 4 days before or after, the symptomatic period, either at the central laboratory or at a local testing facility (using an acceptable test):
 - Fever;
 - New or increased cough;
 - New or increased shortness of breath;
 - Chills;
 - New or increased muscle pain;
 - New loss of taste or smell;
 - Sore throat;
 - Diarrhea;
 - Vomiting.
- Confirmed severe COVID-19 (FDA definition⁴¹): confirmed COVID-19 and presence of at least 1 of the following:
 - Clinical signs at rest indicative of severe systemic illness (RR ≥30 breaths per minute, HR ≥125 beats per minute, SpO₂ ≤93% on room air at sea level, or PaO₂/FiO₂
 300 mm Hg);
 - Respiratory failure (defined as needing high-flow oxygen, noninvasive ventilation, mechanical ventilation, or ECMO);
 - Evidence of shock (SBP <90 mm Hg, DBP <60 mm Hg, or requiring vasopressors);
 - Significant acute renal, hepatic, or neurologic dysfunction;
 - Admission to an ICU;
 - Death.
- Confirmed severe COVID-19 (CDC definition⁴²): confirmed COVID-19 and presence of at least 1 of the following:
 - Hospitalization;
 - Admission to the ICU;

- Intubation or mechanical ventilation;
- Death.

The DMC may recommend modification of the definition of severe disease according to emerging information.

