Initially, sentinel cohorts (sponsor open-label) of 5 participants per group will be enrolled. An IRC and site representatives will review all reported AEs and reactogenicity e-diary data from the sentinel cohorts collected through Day 7 to allow expanded enrollment of an additional 25 participants per group upon confirmation of an acceptable safety assessment. If the safety assessment is considered not to be acceptable, the protocol may be amended to include a further sentinel cohort employing 50-µg dose levels of BNT162b2, BNT162b2 OMI, and a combination of BNT162b2 and BNT162b2 OMI (25 µg each).

Number of Participants

Substudy A will include 10,000 participants.

Substudy B will include up to 1500 participants.

Substudy C will include up to 150 participants.

Substudy D will include up to 1420 participants.

Substudy E will include up to 2910 participants.

Substudy F will include up to 180 participants.

Data Monitoring Committee or Other Independent Oversight Committee

An external DMC will be formed and will review cumulative unblinded data throughout the study.

Substudy C will utilize a DMC that will be used to review safety and immunogenicity data in the first approximately 100 participants with available immunogenicity data (~50 participants in each dose level of BNT162b2)7 days after the third dose.

Substudies E and F will utilize an IRC that will be used to review all reported AEs and reactogenicity data collected through Day 7 from all participants enrolled in the sentinel cohorts to evaluate if enrollment can be expanded in each group.

Statistical Methods:

The statistical methods will be specified in the respective substudy appendices.

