9. STATISTICAL CONSIDERATIONS

Methodology for summary and statistical analyses of the data collected in this study is outlined here and further detailed in a SAP, which will be maintained by the sponsor. The SAP may modify what is outlined in the protocol where appropriate; however, any major modifications of the primary endpoint definitions or their analyses will also be reflected in a protocol amendment.

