10.7.3. Objectives, Estimands, and Endpoints

| Objectives | Estimands | Endpoints |
|--|---|--|
| Primary Efficacy | Primary Efficacy | Primary Efficacy |
| To describe the efficacy of a booster dose of BNT162b2 against confirmed COVID-19 occurring from 7 days after the booster dose through the blinded follow-up period in participants without evidence of past SARS-CoV-2 infection | In participants complying with the key protocol criteria (evaluable participants) and with no serological or virological evidence (prior to 7 days after receipt of the booster dose) of past SARS-CoV-2 infection: 100 × (1 – IRR) [ratio of active vaccine to placebo] | Confirmed COVID-19 incidence from 7 days after the booster dose per 1000 person-years of blinded follow-up |
| To describe the efficacy of a booster dose of BNT162b2 against confirmed COVID-19 occurring from 7 days after the booster dose through the blinded follow-up period in participants with and without evidence of past SARS-CoV-2 infection | In participants complying with the key protocol criteria (evaluable participants) with or without serological or virological evidence (prior to 7 days after receipt of the booster dose) of past SARS-CoV-2 infection: 100 × (1 – IRR) [ratio of active vaccine to placebo] | Confirmed COVID-19 incidence from 7 days after the booster dose per 1000 person-years of blinded follow-up |

| Primary Safety In participants receiving 1 dose of study | Primary Safety |
|---|---|
| In participants receiving 1 dose of study | |
| intervention, the percentage of participants reporting: AEs from the booster dose to 1 month after the booster dose SAEs from the booster dose to 6 months after the booster dose | AEsSAEs |
| Secondary Efficacy | Secondary Efficacy |
| In participants complying with the key protocol criteria (evaluable participants) and with no serological or virological evidence (prior to 7 days after receipt of the booster dose) of past SARS-CoV-2 infection: 100 × (1 – IRR) [ratio of active vaccine to placebo] | Confirmed severe COVID-19 (based on FDA definition) incidence from 7 days after the booster dose per 1000 person-years of blinded follow-up |

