| In participants complying with the key protocol criteria (evaluable participants) and with or without serological or virological evidence (prior to 7 days after receipt of the booster dose) of past SARS-CoV-2 infection: 100 × (1 – IRR) [ratio of active vaccine to placebo] | Confirmed severe COVID-19 (based on FDA definition) incidence from 7 days after the booster dose per 1000 person-years of blinded follow-up |
| In participants complying with the key protocol criteria (evaluable participants) and with no serological or virological evidence (prior to 7 days after receipt of the booster dose) of past SARS-CoV-2 infection: 100 × (1 – IRR) [ratio of active vaccine to placebo] | Confirmed severe COVID-19 (based on CDC definition) incidence from 7 days after the booster dose per 1000 person-years of blinded follow-up |
| In participants complying with the key protocol criteria (evaluable participants) and with or without serological or virological evidence (prior to 7 days after receipt of the booster dose) of past SARS-CoV-2 infection: 100 × (1 – IRR) [ratio of active vaccine to placebo] | Confirmed severe COVID-19 (based on CDC definition) incidence from 7 days after the booster dose per 1000 person-years of blinded follow-up |
| | Cf1 COVID 10 |
| booster vaccination (at initial randomization or subsequently): | Confirmed COVID-19 incidence per 1000 person-years of follow-up |

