10.7.9.4. Interim Analyses

In this substudy, interim efficacy analyses were originally planned to be performed every 2 months by an unblinded statistical team to inform the timing of administration of BNT162b2 to those originally assigned to placebo. This substudy has been unblinded after the first interim analysis as informed by the outcome of the analysis; follow-up interim analyses are no longer applicable. The first interim analysis was performed after all participants reach 2 months of blinded follow-up. The final efficacy analyses to assess the primary and secondary efficacy objectives are planned to be conducted using complete blinded follow-up period data.

At each interim analysis, the following 2 estimates of VE will be obtained: (1) VE of the BNT162b2 booster group to the nonbooster group (placebo), which is the primary estimand defined for this substudy and directly estimable using the data observed in this substudy, and (2) VE of the nonbooster group (who received a primary series of 2 doses of BNT162b2 approximately 6 months prior to enrollment in this study and did not receive the BNT162b2 booster) relative to an unvaccinated population (never received a BNT162b2 primary series, not observable in this study). These estimates will be obtained using the following derivations.

Let VE_{12} be the VE of the BNT162b2 booster group relative to the nonbooster group, VE_1 be the VE of the BNT162b2 booster group relative to an unvaccinated population, VE_2 be the VE of the nonbooster group relative to an unvaccinated population, IR_1 be the incidence rate of COVID-19 illness in the BNT162b2 booster group, IR_2 be the incidence rate of COVID-19 illness in the placebo booster group, and IR_{θ} be the nonobservable incidence rate in the unvaccinated population;

(1)
$$VE_{12}$$
 can be estimated by observed IR_1 and IR_2 in the study as $VE_{12} = 1 - \frac{IR_1}{IR_2}$;

Since
$$VE_1 = 1 - \frac{IR_1}{IR_0}$$
, $VE_2 = 1 - \frac{IR_2}{IR_0}$

(2) VE_2 can then be estimated by observed IR_1 and IR_2 in the study and an assumed VE_1 as

$$VE_2 = 1 - \frac{IR_2(I - VE_1)}{IR_1}$$
.

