10.7.9.4.2. Data Monitoring Committee or Other Independent Oversight Committee

This substudy will use a DMC. The DMC is independent of the study team and includes only external members. The DMC charter describes the role of the DMC in more detail.

The DMC will be responsible for ongoing monitoring of the safety of participants in the study according to the charter. This may include, but is not limited to:

- Contemporaneous review of related AEs up to 1 month after the booster vaccination
- Contemporaneous review of all SAEs up to 6 months after the booster vaccination
- At the time of the planned interim analyses, and ad hoc if requested by the unblinded team, review of COVID-19 cases for an adverse imbalance of COVID-19 cases and/or severe COVID-19 cases between the vaccine and placebo groups

The recommendations made by the DMC to alter the conduct of the study will be forwarded to the appropriate Pfizer personnel for final decision. Pfizer will forward such decisions, which may include summaries of aggregate analyses of safety data, to regulatory authorities, as appropriate.

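### Substudy A leaves the definition of severe COVID-19, the basis of all four secondary efficacy endpoints, open to change on the advice of a DMC that reviews severe cases by arm

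*Protocol*

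**What the plan says.** Section 10.7.8.1.1 sets out the FDA and CDC definitions of severe COVID-19 and closes with: "The DMC may recommend modification of the definition of severe disease according to emerging information".

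The definitions feed the secondary endpoints in section 10.7.3: "Confirmed severe COVID-19 (based on FDA definition) incidence from 7 days after the booster dose per 1000 person-years of blinded follow-up" and "Confirmed severe COVID-19 (based on CDC definition) incidence from 7 days after the booster dose per 1000 person-years of blinded follow-up". Each is analysed in participants without evidence of past infection, and again in participants with and without it. That makes four endpoints, repeated in section 10.7.9.3.3. There is no other secondary efficacy endpoint.

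On who sees what, the Synopsis (section 1.1) says: "An external DMC will be formed and will review cumulative unblinded data throughout the study". For Substudy A, section 10.7.9.4.2 adds, at the planned interim analyses and ad hoc if requested, "review of COVID-19 cases for an adverse imbalance of COVID-19 cases and/or severe COVID-19 cases between the vaccine and placebo groups".

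On who decides, the same section says: "The recommendations made by the DMC to alter the conduct of the study will be forwarded to the appropriate Pfizer personnel for final decision".

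On timing, section 10.7.9.4 says: "This substudy has been unblinded after the first interim analysis as informed by the outcome of the analysis". It also says that the final analyses of the primary and secondary efficacy objectives are planned on the complete blinded follow-up data.

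**The concern.** An endpoint definition protects an estimate from bias only if it is chosen without knowledge of how the cases fall by arm. Here the body invited to propose a new definition is the one that looks at severe cases by arm, and the trigger is not restricted to outside evidence or pooled data. There is no cut-off such as the first unblinded look, and no statement that results under the original definitions would still be reported. Since unblinding, the sponsor staff who would accept or reject a proposal may know the arm-level results too.

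What is at stake is the credibility of the severe-disease VE estimates. They are descriptive, but section 10.7.4.2.1 says that the study is meant to inform vaccine policy, and severe disease is a result that policy readers will look for. Severe cases are likely to be few, so a definition that moves one or two of them can change the estimate and its interval noticeably.

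**Working it through.** **The text, link by link**

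1. *Does the sentence reach an endpoint?* Yes. It follows the two definitions on which the four secondary endpoints rest (10.7.8.1.1, 10.7.3, 10.7.9.3.3).
2. *Does the proposing body know the arm-level result?* Yes (1.1, 10.7.9.4.2).
3. *Is the deciding body blinded?* No longer assured. The sponsor decides (10.7.9.4.2) and the substudy has been unblinded (10.7.9.4). Even before that, section 10.7.6.2.2 placed a medical monitor who reviews severe cases in the unblinded team supporting the DMC.
4. *Can a change still matter?* Yes. The final secondary analyses are still planned, on cases from the blinded period (10.7.9.4).
5. *Does another provision close the gap?*
   - Section 9 says that "any major modifications of the primary endpoint definitions or their analyses will also be reflected in a protocol amendment". It names primary endpoints only.
   - Section 10.1.1 requires ethics approval of amendments, and health authority approval of substantial ones. That controls and records a change but does not make it independent of the results.
   - Section 8.3.7.1 provides blinded internal reviewers. They protect the classification of individual events under a given definition, not the choice of definition.

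**Checking the interval method**

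Section 10.7.9.3.2 specifies Clopper-Pearson adjusted for surveillance time. With equal surveillance time and *p* the boosted share of all cases, VE = 1 - *p*/(1 - *p*); the exact limits for *p* are put through the same formula. For Table 6 at 70 cases and true VE 70%, *p* = 0.3/1.3 = 0.231. The lower limit exceeds 30% when at most 20 of the 70 cases are boosted, which has probability 0.889. Table 6 states 0.889.

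**Illustration with assumed severe counts**

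The protocol gives no severe count for Substudy A. Two rough figures bracket the order of magnitude, both applied to the 6 + 123 = 129 interim cases in section 2.2.1:

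- Parent study C4591001 had 10 severe cases (2.3) and 8 + 162 = 170 cases (2.2.1). 129 × 10/170 = 7.6. This borrows a share from mostly unvaccinated people, and section 2.3 does not give the counting window for the 10.
- Take the placebo share as 9/162. Scale it by (1 - 0.953)/(1 - 0.913) = 0.54, using the FDA-definition and overall efficacies in section 2.2.1, because everyone in Substudy A has had two doses. 129 × 9/162 × 0.54 = 3.9. This also mixes populations and windows.

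So about 4 to 8 cases, as an assumption.

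| Boosted v placebo | VE | 95% CI |
|---|---|---|
| 1 v 7 | 85.7% | -11.2 to 99.7 |
| 0 v 7 (one boosted case dropped) | 100% | 30.6 to 100 |
| 0 v 6 (one case dropped per arm) | 100% | 15.1 to 100 |
| 2 v 7 (one boosted case added) | 71.4% | -50.1 to 97.1 |
| 2 v 9 (one boosted, two placebo added) | 77.8% | -7.4 to 97.7 |
| 0 v 4 | 100% | -51.5 to 100 |

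With no boosted cases and *n* placebo cases the lower limit is 2 - 40^(1/*n*). For *n* = 4 this is 2 - 2.515 = -0.515; for *n* = 7 it is 2 - 1.694 = 0.306.

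A definition applies to both arms, so the rows that move only a boosted case are the most favourable to the argument. The 0 v 6 row shows that the lower limit can still cross zero when a case is lost from each arm. At a total of 4 cases it cannot: even 0 v 4 leaves the lower limit well below zero, and a change then shows mainly in the point estimate.

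**The case against.** The case for leaving the sentence alone has substance.

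- *The DMC only recommends.* Correct. A reader might infer that the DMC can itself rewrite an endpoint whose result it knows. The documents do not say so: the sponsor decides. After unblinding, though, that separation gives limited protection.
- *There are controls.* Correct in part. The definitions are protocol text, so a change would need an amendment with approval, and the endpoint tables carry the FDA and CDC labels and would have to change too. It would be wrong to say that nothing limits the permission. What these controls do not supply is independence from the results.
- *Nothing is tested.* Correct. Section 10.7.9.1.2 makes every objective descriptive and sets no success criterion. A reader might infer inflated type I error, or that one case could decide a formal claim of protection. Neither follows, because no test exists. Bias in an estimate does not need a test.
- *The risk has largely passed.* Partly right. Further interim analyses no longer apply, so of the two stated occasions for DMC review of severe cases by arm only the ad hoc request remains. The protocol, written after unblinding, still carries both original definitions. But the sentence stands and the final secondary analyses are pending.
- *The SAP or DMC charter may restrict it.* Possibly; neither was available. The point is not that a detail is missing but that the protocol states an open permission.

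**Conclusion.** The point stands as a moderate weakness in design wording. The protocol lets a body with arm-level knowledge of severe cases propose a new definition of the secondary efficacy endpoint, on information of any kind, with the decision taken by a sponsor that is no longer blinded. A change made this way could bias the four descriptive severe-disease VE estimates.

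No alpha is affected, the primary endpoints are untouched, and there is no sign that any change has been made or proposed. The numerical effect is unknown. Under assumed totals of about 8 severe cases and equal surveillance time, moving one boosted case shifts VE by about 14 points and the lower limit by about 40 points. With about 4 cases the interval is too wide for the lower limit to reach zero. The conclusion rests on the wording of the protocol and does not depend on those counts.

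**What to change.** Delete the sentence in section 10.7.8.1.1. If flexibility is wanted, replace it with text to this effect: the FDA and CDC definitions given in this section are fixed for the four secondary efficacy endpoints; any later definition, whether proposed by the DMC or by others, is reported only as a supplementary analysis; and the report states the date on which it was adopted and who had seen unblinded data by then.

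The cost is one sentence in the protocol, with matching wording in the SAP and DMC charter if they repeat the permission. No new data, visits or analyses of the existing endpoints are needed. The downside is small: the sponsor can no longer replace the secondary endpoint definition, but can still report results under a newer one alongside it.
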